Reduction in laboratory markers (number and titer of antibody when available) and/or clinical manifestations of autoimmunity, as evaluated starting from the first year follow up visit and thereafter until the 3-year visit, by organ-specific and systemic autoantibodies, imaging and clinical follow up, compared to clinical history

Reduction in eczema, as evaluated by clinical score according to [Imai et al. 2004](#). Specifically, eczema will be scored by the Investigators based on the following scale:

1. None

2. Transient (mild): Asymptomatic or mild symptoms; additional medical intervention over baseline not indicated (consistent with CTCAE grade 1).

3. Moderate: topical or oral intervention indicated; additional medical intervention over baseline indicated (consistent with CTCAE grade 2).

4. Severe: medically significant but not immediately life threatening; intravenous intervention indicated (consistent with CTCAE grade 3).

Eczema scores over time will be presented in a shift table relative to the baseline score.

f) Improved quality of life

Improved quality of life, measured after the first year of treatment by reduced hospitalization, reduced requirement of drugs, school attendance and social activities. The evaluation will be performed according to patients' age (in particular, social ability with peers will not be evaluated before 2 years of age and sport practice will not be considered before 4 years of age).

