9.8. Modification of eczema and autoimmunity phenomena

Modification of eczema and of autoimmunity laboratory markers and/or clinical manifestations (if present before treatment), as evaluated starting from the first year follow up visit and thereafter until the 3-year visit by organ-specific and systemic autoantibodies, imaging and clinical follow up, as compared to clinical history.

Assessment parameters: clinical evaluation including eczema score ([Imai, 2004](#)) and autoimmunity laboratory tests.

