The percentage of subjects who present at one year after gene therapy with adequate multilineage engraftment defined as $\geq 4\%$ in bone marrow and in peripheral blood cell subpopulations (BM subpopulations: GlyA+, CD15+, CD3+, CD19+, CD56+; PB subpopulations: CD15+, CD19+, CD56+) will be estimated and the 95% Confidence Intervals (CI) of this proportion will also be calculated.

A descriptive analysis of the other secondary efficacy endpoints will be provided.

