9.2 Secondary Efficacy

The secondary efficacy analyses will be based on the ITT population, unless otherwise specified.

Table 8 provides an overview of the planned efficacy analyses.

As part of the overall efficacy evaluation, an exploratory analysis of platelet activation and morphology will be performed on platelets obtained from peripheral blood. The data from these analyses are captured outside the eCRF, and thus the reporting is not covered in this SAP.

Table 8 Overview of Planned Secondary Efficacy Analyses

Endpoint/Parameter/Display Type	Absolute ^[1]				Change from Baseline ^[1]			
	Summary		Individual		Summary		Individual	
	T	F	F	L	T	F	F	L
Longitudinal engraftment and WASP expression	X	X	X	X				
Multilineage Engraftment	X	X	X	X				
Frequency of Severe Infections	X	X			X	X		
Frequency of Bleeding episodes	X	X			X	X		
Autoimmunity phenomena ^[2]	X				X			
Eczema	X		X	X	X			
Quality of life: Social life Requirement of drugs Hospitalization	X		X	X				

T = Table, F = Figure, L = Listing, X = Display generated.

• Summary = Represents TF related to any summaries (i.e. descriptive statistics) of the observed raw data.

• Individual = Represents FL related to any displays of individual subject observed raw data.

^[1] Absolute and change from baseline summaries/listings are combined into a single display.

^[2]: Adverse events potentially related to autoimmunity will be identified via checkbox on the eCRF, "In the opinion of the investigator, is this an autoimmune event?".

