9.2.5 Autoimmunity Phenomena

For pre-treatment, autoimmunity events will be determined from a manual review of medical history; additional data will be retrieved from the eCRF for AEs pre-GT (since AEs were not collected pre-GT).

Adverse events related to autoimmunity are identified by the investigator on the eCRF.

Modification of autoimmunity will be evaluated starting from the first year follow-up visit and at day 180 then every year after gene therapy until final assessment (where data are available) and compared to clinical history. Subjects with positive autoimmunity laboratory tests will be listed and summarised over time.

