16.2 Efficacy

16.2.1 Tables

Number	Title	Analysis Set
14.2.1.1.1	Summary of Overall Survival	ITT
14.2.1.2.1	Summary of Subjects with Adequate Engraftment Findings Over Time - Bone Marrow CD34+ and Periperal Blood CD3+	ITT
14.2.1.2.2	Summary Statistics of Vector Copy Number Evaluation in BM and PB cells	ITT
14.2.1.2.6	Summary Statistics of Percentage of Lentiviral Vector Transduced-Colony Forming Units in Bone Marrow Cells (%LVV+ CFU in BM) Over Time	ITT
14.2.1.2.12	Summary of Time to Adequate Engraftment	ITT
14.2.1.3.1	Summary Statistics of Cells Expressing WASP Assessed by Flow Cytometry Over Time	ITT
14.2.1.4.1	Summary Statistics of T-Cell Function	ITT
14.2.1.5.1	Summary of Subjects with Positive Antigen-Specific Responses to Vaccinations	ITT
14.2.1.5.2	Summary of Number and Rate of IVIG Treatment Required by Treatment Phase	ITT
14.2.1.5.3	Summary of Time to Cessation of Sustained IVIG Therapy	ITT
14.2.1.6.1	Summary of Subjects with Improved Platelet Count Over Baseline at Each Year Post Gene Therapy	ITT
14.2.1.6.2	Summary Statistics of Platelet Count and MPV Data	ITT
14.2.1.6.3	Summary of Shifts in Categorical Platelet Count Data From Baseline to Each Year Post Gene Therapy	ITT
14.2.1.6.4	Summary of Shifts in MPV From Baseline to Each Year Post Gene Therapy	ITT
14.2.1.6.7	Summary of Number and Rate of Platelet Infusions by Treatment Phase	ITT
14.2.1.6.8	Summary of Time to Cessation of Sustained Platelet Infusion Therapy	ITT
14.2.2.1.1	Summary of Subjects with Adequate Multilineage Engraftment Findings at Each Year Post Gene Therapy	ITT
14.2.2.2.1	Summary of Severe Infections and All Bleeding Events	ITT
14.2.2.2.3	Summary of Number and Rate of Bleeding Events by Treatment Phase and Severity	ITT
14.2.2.2.4	Summary of Number and Rate of Severe Infections Events by Treatment Phase	ITT

14.2.2.2.6	Summary of Number and Rate of Bleeding Events (Defined from Haemorrhages (SMQ)) by Treatment Phase and Severity	ITT
14.2.2.3.1	Summary of Number of Subjects with Positive Autoimmunity Test	ITT
14.2.2.4.1	Eczema Score Shift Table	ITT
14.2.2.5.1	Summary of Social Life Data Over Time	ITT
14.2.2.5.2	Summary Statistics of Lansky/Karnofsky Performance Index	ITT
14.2.2.6.1	Summary of Days and Rate of Hospitalisation by Treatment Phase	ITT
14.2.3.1.1	Summary of Antimicrobial Treatments by ATC Level 1, Preferred Term and Treatment Phase	ITT
14.2.3.1.2	Summary of Number and Rate of Antimicrobial Treatment Required by Treatment Phase	ITT

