16.2.3 Listings

Number	Title	Analysis Set
16.2.6.1	Listing of Overall Survival	ITT
16.2.6.2	Listing of PCR Transduced Cell Evaluation in BM and PB	ITT
16.2.6.3	Listing of Time to Adequate Engraftment of Genetically Corrected Cells	ITT
16.2.6.4	Listing of WASP Expression by Flow Cytometry	ITT
16.2.6.5	Listing of WASP Expression by Western Blot	ITT
16.2.6.6	Listing of T-Cell Proliferation Responses	ITT
16.2.6.7	Listing of Vaccinations and Subsequent Immunology Evaluations	ITT
16.2.6.8	Listing of Subjects with Positive Antigen-Specific Responses to Vaccinations	ITT
16.2.6.9	Listing of Platelet Count and MPV Data	ITT
16.2.6.10	Listing of Severe Infections	ITT
16.2.6.11	Listing of Bleeding	ITT

16.2.6.12	Listing of Eczema Score	ITT
16.2.6.13	Listing of Positive Autoimmunity Evaluation Data by Visit	ITT
16.2.6.14	Listing of Quality of Life Data	ITT
16.2.6.15	Listing of Bone Marrow Morphology and Karyotype Data	ITT
16.2.6.16	Listing of Bone Marrow Immunophenotype and Colony Forming Unit Data	ITT
16.2.6.17	Listing of Peripheral Blood Immunophenotype Data	ITT
16.2.6.18	Listing of Peripheral Blood Immunophenotype Subpopulations Outside Normal Reference Ranges	ITT
16.2.6.19	Listing of Serum Immunoglobulin Data	MS
16.2.6.20	Listing of Lymphocyte Proliferative Response	ITT
16.2.6.21	Listing of Patients Requiring IVIG Infusion	ITT
16.2.6.22	Listing of Replication Competent Lentivirus Evaluations	MS
16.2.6.23	Listing of TCR Repertoire by Flow Cytometry	ITT
16.2.6.24	Listing of Immune Response to Transgene	MS
16.2.6.25	Listing of Zhu Clinical Score	ITT
16.2.6.26	Listing of Positive Microbiological Evaluations	ITT
16.2.6.27	Listing of Antibodies to Pathogens	ITT

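### The autoimmunity laboratory endpoint is a reduction in number and titre of autoantibodies, but the SAP's only laboratory summary table counts subjects with a positive test and defines no within-patient change

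*SAP*

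**What the plan says.** Protocol 4.3.2(e) gives the endpoint as "Reduction in laboratory markers (number and titer of antibody when available) and/or clinical manifestations of autoimmunity", judged against the patient's history. Protocol 9.8 is looser and names no metric: "Modification of eczema and of autoimmunity laboratory markers and/or clinical manifestations (if present before treatment". On analysis, Protocol 12.4 says only "A descriptive analysis of the other secondary efficacy endpoints will be provided".

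SAP 9.2.5 says that change in autoimmunity will be assessed at day 180 and at the yearly visits and set against the clinical history. For the laboratory data it then says "Subjects with positive autoimmunity laboratory tests will be listed and summarised over time". Appendix 1 of the SAP lists one laboratory summary table for this endpoint, 14.2.2.3.1, "Summary of Number of Subjects with Positive Autoimmunity Test", and one listing, 16.2.6.13, "Listing of Positive Autoimmunity Evaluation Data by Visit".

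SAP Table 8 marks a table for autoimmunity under both the absolute and the change-from-baseline columns, with the general note "Absolute and change from baseline summaries/listings are combined into a single display". The row's own footnote concerns adverse events flagged by the investigator. SAP section 14, which records changes from the protocol, does not mention this endpoint.

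**The concern.** The protocol's metric is graded and belongs to the patient: how many autoantibodies, and how strong. The SAP's summary is a count of people. The two can disagree. A patient who loses most but not all of his autoantibodies has improved by the protocol's definition, yet may still be counted as positive.

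This matters because no test or model stands behind the summary. With 8 patients and a descriptive analysis, the choice of summary variable is the analysis. Other endpoints get more. Eczema, the other half of endpoint (e), has a change from baseline and shift tables (SAP 9.2.6), and platelet count has shift tables (SAP 9.1.6). The autoantibody component has neither.

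**Working it through.** The plan states no figure for this endpoint, so there is nothing to reproduce. The check compares the protocol's metric with what each SAP output can show.

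**Inputs from the documents**
- Panel (Protocol 7.1(k) and 7.2(j)): anti-platelet, p-ANCA, c-ANCA, anti-DNA, AMA, ASMA, LKM, direct Coombs, indirect Coombs and ANA. That is 10 tests, with ENA added only if ANA is positive.
- Planned sample: 8 patients (SAP section 6).
- Table layout: left to a separate shells document (SAP section 8), which is not available here.

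**Assumption.** The documents give no baseline number of positive autoantibodies per patient. For illustration, take one patient with 6 positives at baseline, a range of values at year 3, and no new antibodies.

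| Positives, baseline to year 3 (assumed) | Change in number (protocol metric) | Single any-positive row | One row per antibody |
|---|---|---|---|
| 6 to 5 | -1 (1/6 = 17% fall) | 1 to 1, no change | 1 row loses this patient |
| 6 to 3 | -3 (3/6 = 50% fall) | 1 to 1, no change | 3 rows lose this patient |
| 6 to 1 | -5 (5/6 = 83% fall) | 1 to 1, no change | 5 rows lose this patient |
| 6 to 0 | -6 (100% fall) | 1 to 0, improved | 6 rows lose this patient |

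**What each output shows**
1. *Any-positive row.* It registers only complete clearance. Every partial fall, here from 17% to 83%, leaves the count unchanged.
2. *One row per antibody.* The fall in number appears at group level, but patients are not paired. If one patient loses ANA and another gains it, the ANA row stays at 1. Titre is absent under either layout.
3. *Listing 16.2.6.13.* A fall from 6 entries to 1 can be read off for an individual patient. By its title, however, the listing holds positive results only, so a test that became negative and a test that was not done both disappear. With 1 positive at year 3, the listing looks the same whether all 10 tests were run or only 4. The SAP does not say whether titres are shown.
4. *Table 8.* The change-from-baseline mark could cover this, but neither 9.2.5 nor Appendix 1 says which quantity changes.

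No SAP text, table or figure derives the number of positive antibodies per patient, a change in titre, or a classification of patients as decreased, unchanged or increased.

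**The case against.** The best case for the plan has four parts.

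- **The SAP does more than count.** It also lists positive results by visit, calls for comparison with clinical history, and marks a change-from-baseline table. In 8 patients a reader can follow each one through the listing. This stands as far as it goes: the defect is an undefined change variable, not a complete absence of follow-up over time. The listing still cannot separate negative from untested.
- **The any-positive layout is not stated.** The title of Table 14.2.2.3.1 fits one row per antibody equally well, and the shells may say so. This stands, so the complete masking in the example is conditional on the layout. A per-antibody table would still give no paired change and no titre.
- **The protocol wording is permissive.** Titre counts only when available, and laboratory markers are joined to clinical manifestations by and/or. Clinical autoimmunity has its own outputs: events by treatment phase (SAP 10.2.2.3, Tables 14.3.2.2.10 and 14.3.2.2.14) and a manual review of history before treatment (SAP 9.2.5). A reader might infer that the secondary objective on autoimmunity cannot be answered at all. The documents do not support that, because the clinical component is summarised separately.
- **Nothing is tested.** A reader might want to express the problem as lost power of a positive/negative comparison against a comparison of antibody numbers. That does not describe this trial: the endpoint is descriptive, the SAP plans no test for it, and SAP section 7 says the study is not powered.

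**Conclusion.** The point holds in a limited form. The protocol names a reduction in number and, where available, titre. The SAP's only laboratory summary is the number of subjects with a positive test, the change-from-baseline entry in Table 8 has no defined variable, and section 14 does not acknowledge the difference. Partial reductions within a patient may be visible only in a listing restricted to positive results. Under a single any-positive row they would not appear in the summary table at all.

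The size is modest: one laboratory component of a descriptive secondary endpoint in 8 patients. How much would be hidden in practice cannot be computed, since the documents give neither baseline antibody numbers nor the table shell. The conclusion rests on the SAP text and output titles as written. The 6-antibody example is an assumption that shows the mechanism and does not estimate an effect.

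**What to change.** In SAP 9.2.5 and Table 14.2.2.3.1, for each scheduled visit:

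- Give the number of positive autoantibodies per patient, among the antibodies tested at both baseline and that visit.
- Give the paired change from baseline: median, range, and the number of patients decreased, unchanged and increased.
- Add the change in titre from baseline where titres were recorded, with the number of patients contributing.
- Keep the count of positive subjects as a supporting row, and state whether it is any-positive or per antibody.

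In Listing 16.2.6.13, show negative and not-tested results as well as positives. In Table 8, tie the change-from-baseline mark to the variable defined above.

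The panel is already scheduled in the protocol, so the cost is SAP wording and a few table rows. Titre data may be incomplete: the protocol anticipates this, and the documents do not establish that titres are held in the database. If they are not, the SAP should say so in section 14.

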9.2.6 Eczema

The severity of eczema will be assessed by an eczema score as part of the clinical examination. Each subject is assigned one of four scores at each visit: 1 for None, 2 for Transient, 3 for moderate and 4 for severe. Reduction in eczema will be evaluated by the change from baseline in eczema score at each year after gene therapy.

Shift tables will be produced to display the number and percentage of subjects at each eczema score at baseline and the shift at each year after gene therapy. The longitudinal profile over time of the eczema score will be described by means of a listing and a plot.

9.2.7 Quality of life

Quality of life will be assessed according to whether the subject was living in a protected environment, attending school or kindergarten, social ability with peers and participation in sport, as relevant for age.

For subjects who were living in a protected environment at baseline, time to not living in a protected environment will be calculated as:

Time to not living in a protected environment = date of first visit where no longer living in a protected environment – date of baseline visit

For subjects who were not living in a protected environment at baseline, the time will not be calculated.

Lansky play-performance rating (for subjects < 16) or Karnofsky performance status (for subjects ≥ 16) will also be assessed. A summary table will be produced and individual profiles will be plotted over time. Ratings are assigned based upon the below scale for assessment of play and activity in the previous week:

Table 9 Karnofsky/Lansky Performance Ratings

Rating	Lansky Description	Karnofsky Description
100	Fully active, normal	Normal; no complaints; no evidence of disease.
90	Minor restrictions with strenuous physical activity	Able to carry on normal activity; minor signs or symptoms of disease.
80	Active, but gets tired more quickly	Normal activity with effort; some signs or symptoms of disease.
70	Both greater restriction of, and less time spent in, active play	Cares for self; unable to carry on normal activity or to do active work
60	Up and around, but minimal active play; keeps busy with quieter activities	Requires occasional assistance, but is able to care for most of their personal needs
50	Lying around much of the day, but gets dressed; no active play; participates in all quiet play and activities	Requires considerable assistance and frequent medical care
40	Mostly in bed; participates in quiet activities	Disabled; requires special care and assistance
30	Stuck in bed; needs help even for quiet play	Severely disabled; hospital admission is indicated although death not imminent
20	Often sleeping; play is entirely limited to very passive activities	Very sick; hospital admission necessary; active supportive treatment necessary
10	Does not play nor get out of bed	Moribund; fatal processes progressing rapidly
0	Unresponsive	Dead

The number (and percentage) of subjects living in a protected environment, attending kindergarten/school and practising sport will be summarised.

A listing of complete quality of life assessment will be produced.

Although not a quality of life measure, the Zhu score, a measure of severity of disease, of subjects over time will be presented in a listing.

9.2.8 Hospitalisations

Hospitalisations will be recorded on the Relevant Medical History page, Concomitant Diseases page and Adverse Event page. Days of hospitalisation will be calculated from the admission date and discharge date from the eCRF. Subjects may be hospitalised for multiple AEs. Therefore, overlapping periods of hospitalisation will only be counted once.

The number of days of hospitalisation and rate of hospitalizations per patient year observation will be summarised for the pre-treatment phase (12 months prior to gene therapy), post-treatment phases (as defined in Table 3) and the overall phase post 6 months after gene therapy. Rates will be provided along with confidence intervals. A listing will also be created of hospitalisations.

9.3 Exploratory Efficacy

9.3.1 Analysis of antimicrobial treatment

A summary of the antimicrobial medications per treatment phase (Table 3) will be presented along with the rate of treatments per year of observation.

A summary of time to sustained antimicrobial treatment discontinuation will be produced for subjects who no longer need antimicrobial treatment. The cessation of sustained treatment is defined as a period of 3 months post gene therapy without antimicrobial treatment. The time to discontinuation will be presented in a table and Kaplan Meier plot including median time to discontinuation and 95% confidence interval.

A listing will also be created of positive microbiological evaluations.

9.3.2 Platelet Activation Profile and Morphology

The analysis and reporting of this exploratory endpoint will be detailed in a separate document that will be summarised within and appended to the CSR.

10 Safety Analyses

10.1 All outputs for safety outcomes will be based on the MS Set. Planned Primary Safety Analyses

Table 10 provides an overview of the planned analyses.

Table 10 Overview of Planned Primary Safety Analyses

[Endpoint / Parameter/ Display Type]	Raw Data			
	Summary		Individual	
	T	F	F	L
Safety of reduced conditioning regimen				
Prolonged aplasia based on ANC data	Y		Y	Y
Conditioning regimen related non-hematopoietic toxicity	Y			Y
Safety of LVV gene transfer into HSC				
AEs/SAEs within 2 days from infusion	Y			Y
RCL	Y			Y
ACP				Y

T = Table, F = Figure, L = Listing, Y = Yes display generated.

Summary = Represents TF related to any summaries (i.e. descriptive statistics) of the observed raw data.

Individual = Represents FL related to any displays of individual subject observed raw data

10.1.1 Safety of Reduced Conditioning Regimen

Prolonged aplasia will be assessed based on Absolute Neutrophil Count (ANC) data collected at the Day 60 visit together with bone marrow recovery and back-up administration data (recorded in Adverse Event or Concomitant Medications page if there are any) for each subject. A listing of ANC data collected at Day 60 visit by subject will be generated. This will include all ANC data assessed in the visit window for Day 60 (from Day 47 to Day 76, Section [7.3.1](#)). The longitudinal profile of ANC for the whole post treatment phase as well as from baseline to 100 days post treatment will be described by means of two plots of individual patient data.

Regimen related non-hematopoietic toxicity will be assessed based on the clinical and laboratory data collected during the first 100 days post gene therapy (this is based on assessment of AEs with National Cancer Institute (NCI) CTCAE grade ≥ 2 for clinical features and NCI CTCAE grade ≥ 3 for laboratory parameters) for each subject. A summary and listing of clinical features NCI CTCAE grade ≥ 2 and laboratory features NCI CTCAE grade ≥ 3 during the first 100 days after gene therapy will be generated. Events are included based on the onset days from infusion.

To increase the informative clinical value of conditioning-related AEs, the 100 days period will be further stratified in three phases:

- Day 0-30
- Day 31 to Day 60
- Day 61 to Day 100

